As there were no differences in safety or tolerability between the 2 dosing regimens and the higher regimen appeared to be more effective, the 3 mg/kg dose was selected for this Phase 3 open-label extension study.

The infusions were generally well tolerated at all doses with most IRR being mild to moderate and very few AE outside the infusion window. Patients with ISM, CU, severe AC, mast cell gastritis, and EG/EoD have received monthly doses of 1 mg/kg and 3 mg/kg AK002. Subsequent infusions in multiple dose cohorts were associated with fewer IRR when compared with the first infusion.

4. Study Objectives

The objective of the study is to generate open-label, longer-term safety, tolerability, and efficacy follow-up data in patients with EG and/or EoD who completed Study AK002-016 or Study AK002-012. In addition, this study provides patients randomized to placebo in AK002-016 the option to receive active dosing.

5. Study Design

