9.6 Study Drug Administration

Specific instructions on administration and supplies required for administration are detailed in the Pharmacy Manual. In general, study drug will be infused through a peripheral vein intravenous set. The intravenous line should be kept open before and after the infusion with sufficient quantities of 0.9% NaCl to assure patency.

A volume of 100 mL* of the calculated dose of study drug will be infused over at least 4 hours on Extension Day 1, over at least 2 hours on Extension Days 29 (± 3), 57 (± 3), 85 (± 3), 113 (± 3), and 141 (± 3) and over at least 1 hour from Extension Day 169 (± 3) and onwards. If the infusion is slowed or interrupted, the time may be extended longer than 4 hours, as long as it does not exceed 8 hours.

* Due to the rounding of the total infusion volume by some programmable infusion pumps, an infusion of 99 mL to 101 mL will be considered a complete infusion and will not be recorded as a deviation of the study.

Due to programming limitations of some infusion pumps, all volumes associated with the infusion may be rounded to the nearest 1/10th mL.

For the first infusion of study drug, patients will be premedicated with 80 mg oral prednisone (or approved equivalent) 12–24 hours prior to the start of the study drug infusion. For subsequent infusions, premedication may only be used at the discretion of the Investigator and with the written approval of the Medical Monitor.

The IV infusion may be interrupted and/or the rate may be reduced if a patient has an IRR. The time the infusion is initiated/concluded (including any interruptions) will be documented in the eCRF. If the infusion is restarted after an interruption, the infusion must be completed within 8 hours of preparation. Administration will be discontinued if, in the opinion of the Investigator,

an interrupted infusion cannot be restarted for safety reasons or if the infusion cannot be completed within 8 hours of preparation. Administration will also be discontinued in any patient experiencing a serious adverse event during the course of the infusion.

The patient will be observed at least 1 hour after the end of each infusion, as per Investigator discretion.

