12.2 Extension Day 1 – First Day of Dosing

The following procedures will be performed prior to study drug infusion:

- Confirm continuing eligibility for the study.
- Activate patient access to ViedocME website and instruct patient on use of the website to complete the questionnaire(s). Use the ePRO Teaching Tool (Appendix 4) to remind patients on the use of the electronic platform.
- Have patient complete SF-36 Health Survey. Obtain from last study visit of AK002-016 if the visit occurred within 28 days prior to Extension Day 1.
- Determine body weight (in kg).
- Enter PID and body weight (in kg) into IRT.
- Document any changes in baseline diet. Obtain from last study visit of AK002-016 if the visit occurred within 28 days prior to Extension Day 1.

- Collect vital signs within 30 minutes of the start of the infusion.
- Perform symptom-directed physical examination, as needed. Obtain from last study visit of AK002-016 if the visit occurred within 28 days prior to Extension Day 1.
- Collect blood samples for CBC, blood chemistry, IgE, ADA, and PK. Obtain from last study visit of AK002-016 if the visit occurred within 28 days prior to Extension Day 1. Differential cell counts from AK002-016 will remain blinded.
- Collect urine for urinalysis. Obtain from last study visit of AK002-016 if the visit occurred within 28 days prior to Extension Day 1.
- Perform urine pregnancy test. Obtain from last study visit of AK002-016 if the visit occurred within 28 days prior to Extension Day 1.
- The study pharmacist will prepare study drug at **3 mg/kg** using the body weight obtained at the visit or the day prior to Extension Day 1. The final combined volume of the IV bag of study drug + 0.9% NaCl will be **120 mL**.

Note: **100 mL** of the calculated volume of study drug/NaCl mixture will be administered to the patient. The extra 20 mL is to be used to prime the IV infusion line during the preparation of the IV line or to be left over in the infusion bag/tubing when the infusion is completed.

Procedures associated with the infusion of study drug include:

- Infuse 100 mL of study drug over at least 4 hours using an infusion pump. Refer to the Pharmacy Manual for infusion rates. Record the start and stop times of the infusion including any times the infusion is interrupted.
- Collect vital signs within 30 minutes after the start of infusion.

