- An unscheduled ADA blood sample may be obtained if an immunogenicity-related AE is suspected. If anaphylaxis is suspected, collect a sample of blood for plasma histamine and tryptase levels within 1–2 hours of the onset of symptoms.

The following procedures will be performed after study drug infusion:

- Collect vital signs within 30 minutes after the end of infusion.
- Collect CBC with differential 1 hour (± 15 minutes) after the end of infusion.
- Observe the patient for at least 1 hour after the end of infusion.

Concomitant medication use and AE (including AESI and SAE) will be documented throughout the clinic visit.

12.3 Extension Day 29 (± 3) – Dose 2

The following procedures will be performed prior to study drug infusion:

- Have patient complete the SF-36 Health Survey.
- Determine body weight (in kg).
- Enter PID and weight (in kg) into IRT.
- Document any changes in baseline diet.
- Collect vital signs within 30 minutes prior to the start of infusion.
- Collect urine only if patient is of childbearing potential. Conduct a urine pregnancy test.
- Perform symptom-directed physical examination, as needed.
- Collect blood samples for CBC and chemistry.
- The study pharmacist will prepare study drug at **3 mg/kg** using the body weight obtained at the visit. The final combined volume of the IV bag of study drug + 0.9% NaCl will be **120 mL**.

Note: **100 mL** of the calculated volume of study drug/NaCl mixture will be administered to the patient. The extra 20 mL is to be used to prime the IV infusion line during the preparation of the IV line or to be left over in the infusion bag/tubing when the infusion is completed.

Procedures associated with the infusion of study drug include:

- Premedication only to be administered with the written approval of the Medical Monitor.
- Infuse 100 mL of study drug using an infusion pump over at least 2 hours on Extension Day 29. Refer to the Pharmacy Manual for infusion rates. Record the start and stop times of the infusion including any times the infusion is interrupted.
- Collect vital signs within 30 minutes after the start of infusion.
- An unscheduled ADA blood sample may be obtained if an immunogenicity-related AE is suspected. If anaphylaxis is suspected, collect a sample of blood for plasma histamine and tryptase levels within 1–2 hours of the onset of symptoms.

The following procedures will be performed after study drug infusion:

- Collect vital signs within 30 minutes of the end of infusion.

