Note: **100 mL** of the calculated volume of study drug/NaCl mixture will be administered to the patient. The extra 20 mL is to be used to prime the IV infusion line during the preparation of the IV line or to be left over in the infusion bag/tubing when the infusion is completed.

Procedures associated with the infusion of study drug include:

- Premedication only to be administered with the written approval of the Medical Monitor.
- Infuse 100 mL of study drug using an infusion pump over at least 1 hour, depending on the Investigator's discretion and tolerance to prior infusions. Refer to the Pharmacy Manual for infusion rates. Record the start and stop times of the infusion including any times the infusion is interrupted.
- Collect vital signs within 30 minutes after the start of infusion.
- An unscheduled ADA blood sample may be obtained if an immunogenicity-related AE is suspected. If anaphylaxis is suspected, collect a sample of blood for plasma histamine and tryptase levels within 1–2 hours of the onset of symptoms.

The following procedures will be performed after study drug infusion:

- Collect vital signs within 30 minutes of the end of infusion.
- Collect CBC with differential 1 hour (± 15 minutes) after the end of infusion.
- Observe the patient for at least 1 hour after the end of infusion.

Concomitant medication use and AE (including AESI and SAE) will be documented throughout the clinic visit.

12.9 Extension Day 197 (± 3) – Dose 8

The following procedures will be performed prior to study drug infusion:

- Have patient complete the SF-36 Health Survey.
- Determine body weight (in kg).

- Enter PID and weight (in kg) into IRT.
- Document any changes to baseline diet. Changes are allowed after the seventh dose has occurred and will be documented in the CRF.
- Collect vital signs within 30 minutes prior to the start of infusion.
- Collect urine only if patient is of childbearing potential and perform urine pregnancy test.
- Perform symptom-directed physical examination, as needed.
- Collect blood samples for CBC, chemistry, PK, and ADA.
- The study pharmacist will prepare study drug at **3 mg/kg** using the body weight obtained at the visit. The final combined volume of the IV bag of study drug + 0.9% NaCl will be **120 mL**.

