13.4 Infusion-Related Reactions

All AE considered by the Investigator *to be related to the infusion* of the biological substance and occurring within 24 hours of the start of the study drug infusion, should be captured as 1 AE, termed “Infusion-Related Reaction” (IRR).

Common symptoms of IRR include:

• Flushing	• Nausea
• Chills	• Vomiting
• Back or abdominal pain	• Sweating
• Chest discomfort or tightness	• Fever
• Dizziness	• Urticaria
• Shortness of breath	• Pruritus
• Headache	• Bronchospasm
• Hypotension or hypertension	

All symptoms experienced by a patient during an IRR will be listed in the eCRF under 1 IRR, unless the Investigator believes a symptom is not part of the IRR, in which case it will be recorded separately. The start time of the IRR will be captured as the start time of the first symptom, and the end time of the IRR will be captured as the end time of the last symptom.

Any medications used within 24 hours of an infusion for the treatment of an IRR are not considered prohibited medications nor deviations from the protocol.

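### Infusion reactions are defined over 24 hours, but required observation covers only the first 5, 3 or 2 hours and no query is scheduled before the next visit, so later reactions may be missed and rates by dose may not be comparable

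*Combined protocol and SAP*

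**What the plan says.** **Definition.** Section 13.4 groups into one IRR all events the investigator relates to the infusion and "occurring within 24 hours of the start of the study drug infusion". The IRR's start time is that of its first symptom.

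**Infusion time.** Dose 1 (Section 12.2): "Infuse 100 mL of study drug over at least 4 hours using an infusion pump". Dose 2 (Section 12.3): "Infuse 100 mL of study drug using an infusion pump over at least 2 hours on Extension Day 29", with the same minimum in Sections 12.4 to 12.7. Dose 7 (Section 12.8): "Infuse 100 mL of study drug using an infusion pump over at least 1 hour", and likewise in 12.9 and 12.11. Section 9.6 agrees: "over at least 1 hour from Extension Day 169 (± 3) and onwards".

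**Observation.** Every dosing visit carries the step "Observe the patient for at least 1 hour after the end of infusion". Section 9.6 words it as "The patient will be observed at least 1 hour after the end of each infusion, as per Investigator discretion".

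**Event collection.** The dosing-visit steps have AEs documented over the course of the visit. Section 13.1 keeps AE recording open from the first dose to Day 561, whether staff ask or the patient volunteers. Neither Table 1 nor Section 12 schedules a question about reactions once the 24 hours have passed.

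**Analysis.** Section 15.5 lists patient-incidence tables of TEAEs, including those of special interest. None is by infusion number, and Section 15 rules out formal inference.

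**The concern.** IRR is the most common TEAE in earlier studies (Section 2.3) and an event of special interest (Section 13.3), in a study whose objective includes longer-term safety and tolerability (Section 4). To be classed as an IRR, an event needs an onset within 24 hours and a relatedness judgement. For a reaction that starts at home and is not volunteered, both would be reconstructed at a visit two to four weeks later. The event may then be forgotten, or recorded as something other than an IRR. Late notice also weakens the event-triggered antibody sample in Section 11.4.6, since scheduled sampling falls only on Days 1, 197 and 512.

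The observed part of the window also shrinks as infusions shorten. Section 3 reports from earlier work that "Subsequent infusions in multiple dose cohorts were associated with fewer IRR when compared with the first infusion", so readers will look for the same pattern here. If the means of finding IRRs changes with dose number, a difference between doses need not reflect a difference in tolerability.

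**Working it through.** The plan gives no figure to reproduce, so the check is direct arithmetic followed by a sensitivity calculation on stated assumptions.

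**1. Required coverage of the window.** Inputs: minimum infusion times (Sections 9.6 and 12.2 to 12.11), at least 1 hour of observation, and a 24-hour window from infusion start (Section 13.4). Covered hours = minimum infusion + 1; share = covered hours / 24.

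| Doses | Covered | Share of 24 h | Not covered |
|---|---|---|---|
| 1 | 4 + 1 = 5 h | 20.8% | 19 h |
| 2–6 | 2 + 1 = 3 h | 12.5% | 21 h |
| 7–18 | 1 + 1 = 2 h | 8.3% | 22 h |

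Over all 18 doses: 5 + 5×3 + 12×2 = 44 of 18×24 = 432 window-hours, or 10.2%. These are minimums.

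**2. Next scheduled contact.** Doses fall every 28 days from Day 1 to Day 477. After Dose 8 (Day 197) the Day 211 EGD comes 14 days later, and AEs are collected there. After the other 17 doses the gap is 28 days. For Dose 18 that is Day 505 − Day 477 = 28; the body of Section 12.12 says 14 days, and the two must be reconciled.

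**3. What the diary can pick up.** Section 13.4 lists 15 IRR symptom entries. The ten-question diary (Appendix 1) touches three: abdominal pain, nausea and vomiting. It has no item for flushing, chills, headache, dizziness, fever, urticaria, pruritus, chest tightness or shortness of breath. Patients are told to rate their EG/EoD symptoms. The extra questions on asthma, atopic dermatitis and dysphagia reach subsets only. No text has diary entries reviewed for AEs.

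**4. Size and direction (assumptions, not data).** The documents give no onset distribution. Take onset as exponential with mean parameter m, truncated at 24 hours, and let T be the covered hours. The share of IRRs starting after the required observation is

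late share = (e^(−T/m) − e^(−24/m)) / (1 − e^(−24/m)).

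For m = 2 and T = 5, e^(−2.5) = 0.082, giving 8.2%.

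| Assumed onset | Dose 1 | Doses 2–6 | Doses 7–18 |
|---|---|---|---|
| Fixed mean 1 h | 0.7% | 5.0% | 13.5% |
| Fixed mean 2 h | 8.2% | 22.3% | 36.8% |
| Fixed mean 4 h | 28.5% | 47.1% | 60.6% |
| Mean = half the infusion time | 8.2% | 5.0% | 1.8% |
| Mean = infusion time | 28.5% | 22.3% | 13.5% |

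The late share rises with dose number if onset follows the clock, and falls if it scales with infusion length. The under-count is late share × (1 − share reported later). For example, a 5% late share gives 5.0%, 2.5% or 0.5% when 0%, 50% or 90% are later reported.

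**5. Which onset category is comparable between doses.** Onset during the infusion or the hour after it spans 5, 3 or 2 hours. With a fixed mean of 2 hours it holds 100 − 8.2 = 91.8%, 77.7% and 63.2% of IRRs although nothing about onset differs between doses. A window of the first 2 hours from infusion start holds 63.2% at every dose. If the mean equals infusion time, that same window holds (1 − e^(−2/m)) / (1 − e^(−24/m)) = 39.4%, 63.2% and 86.5% (m = 4, 2, 1). A common window therefore removes the effect of unequal observation, but not a true shift in onset, and needs the 24-hour count beside it.

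**The case against.** Several counter-arguments stand.

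- **Late reactions remain recordable.** Collection runs to Day 561 and includes volunteered and elicited events (Sections 13.1 and 13.7). Missed events are a risk, not an established under-count.
- **The hours are floors.** The investigator may observe for longer, and infusions may be slowed or interrupted, so patients who have reacted before may be watched longer.
- **The only timing evidence points to few late events.** Section 3 says AEs beyond the infusion window were rare. It does not define that window, give a rate, or say how late events were sought, so it reassures without settling the matter.
- **No comparison between infusions is planned.** One would be confounded anyway: 80 mg prednisone is routine only before Dose 1, and patients from the active arm of AK002-016 have already had six infusions. Comparability therefore concerns how results may be read, not a planned test.

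A reader might infer that under-counting grows as infusions get faster. The documents do not support that: the direction reverses if onset scales with infusion length. A reader might also infer that the pattern reported in Section 3, of fewer IRRs after the first infusion, was produced by shorter observation. That pattern comes from other studies whose infusion and observation times are not given here, so this schedule cannot explain it.

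**Conclusion.** The gap is real: a 24-hour definition, required observation of at least 5, 3 or 2 hours (21%, 12.5% and 8% of the window), and no solicited query until a visit 14 days later (Dose 8) or about 28 days later (the rest). IRRs that start after discharge rest on volunteered report or delayed recall and are at risk of being missed or misclassified.

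How many is unknown, since the documents give neither onset times nor recall rates; the shares in the second table are illustrations under assumed distributions. The supportable conclusion on dose number is that IRR rates may not be comparable, with the direction undetermined. This is a data-collection weakness that is cheap to close. It does not undermine the study.

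**What to change.** **Collection (Sections 12.2 to 12.9 and 12.11, and Table 1).** Add one yes/no ViedocME item on the day after each infusion: any new symptom in the 24 hours from the start of that infusion. Ask it identically at every dose, and open it only once the 24 hours have passed. Anchoring to infusion start matters because ordinary diary recall, counted back from the time of completion, could miss the hours just after discharge. A positive answer prompts the site to record onset time and relatedness.

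**Description (Section 15.5).** If IRRs are described by infusion number, use the start times already collected. Show a window common to all doses, such as the first 2 hours from infusion start, alongside the full 24-hour count. Do not base the comparison on onset during infusion or the 1-hour observation, because that category changes length with dose.

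**Cost.** One diary item on up to 18 days per patient, occasional site follow-up, and a table from existing data if IRRs are shown by infusion. The reported IRR rate may rise because more is asked, which should be noted when it is set beside earlier studies. Infusion and observation times are unchanged.

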12.10 Extension Day 211 (± 3) – First EGD

The on-treatment EGD should be completed 14 (± 3) days after the eighth dose of study drug. All risks and associated details regarding the EGD procedure will be discussed with the patient by the EGD provider.

The following procedures will be performed:

- Patient should arrive fasting for the EGD procedure as specified by instructions from the EGD provider.
- Collect AE, SAE, and changes in concomitant medications. Capture all concomitant medications provided to the patient during the EGD.
- Perform the EGD with biopsy following procedures provided by Allakos and all EGD facility standard operating procedures.

12.11 Extension Day 225 to Day 477 (± 3) – Doses 9 to 18

Extension Days 225, 253, 281, 309, 337, 365, 393, 421, 449, and 477

The following procedures will be performed prior to study drug infusion:

- Have patient complete the SF-36 Health Survey.
- Determine body weight (in kg).
- Enter PID and weight (in kg) into IRT.
- Document any changes to baseline diet.
- Collect vital signs within 30 minutes prior to the start of infusion.
- Collect urine only if patient is of childbearing potential and perform urine pregnancy test.
- Perform symptom-directed physical examination, as needed.
- Collect blood samples for CBC and chemistry.
- The study pharmacist will prepare study drug at **3 mg/kg** using the body weight obtained at the visit. The final combined volume of the IV bag of study drug + 0.9% NaCl will be **120 mL**.

Note: **100 mL** of the calculated volume of study drug/NaCl mixture will be administered to the patient. The extra 20 mL is to be used to prime the IV infusion line during the preparation of the IV line or to be left over in the infusion bag/tubing when the infusion is completed.

Procedures associated with the infusion of study drug include:

- Premedication only to be administered with the written approval of the Medical Monitor.
- Infuse 100 mL of study drug using an infusion pump over at least 1 hour, depending on the Investigator's discretion and tolerance to prior infusions. Refer to the Pharmacy Manual for infusion rates. Record the start and stop times of the infusion including any times the infusion is interrupted.
- Collect vital signs within 30 minutes after the start of infusion.

For Early Termination: Perform Safety Follow-up Visit 1, 35 (± 3) days after last dose of study drug or prior to this, if necessary, to ensure compliance with the visit. If patient discontinues the study more than 35 days after last dose of study drug, perform the visit as soon as possible as directed by the Medical Monitor.

12.14 Extension Day 533 (± 3) or 56 (± 3) Days after Last Dose – Follow-up Visit 2

The following procedures will be performed:

- Have patient complete the SF-36 Health Survey.
- Determine body weight.
- Document any changes to baseline diet.
- Collect vital signs.
- Perform symptom-directed physical examination, as needed.
- Collect blood samples for CBC and chemistry.

Concomitant medication use and AE (including AESI and SAE) will be documented throughout the clinic visit.

For Early Termination: Perform Safety Follow-up Visit 2, 56 (± 3) days after last dose of study drug or prior to this, if necessary, to ensure compliance with the visit.

12.15 Extension Day 561 (± 3) or 84 (± 3) Days after Last Dose – Follow-up Visit 3

The following procedures will be performed:

- Have patient complete the SF-36 Health Survey.
- Determine body weight.
- Document any changes to baseline diet.
- Collect vital signs.
- Perform symptom-directed physical examination, as needed.
- Collect blood samples for CBC and chemistry.

Concomitant medication use and AE (including AESI and SAE) will be documented throughout the clinic visit.

For Early Termination: Perform Safety Follow-up Visit 3, 84 (± 3) days after last dose of study drug or prior to this, if necessary, to ensure compliance with the visit.

13. Adverse Event Reporting and Documentation

